Aim 1: To evaluate the feasibility of the LIFT and REAP interventions in patients evaluated for liver transplantation.

Aim 2: To measure the effect of the LIFT and REAP intervention on frailty in patients evaluated for liver transplantation.

Aim 3: To evaluate barriers to the implementation of the LIFT and REAP interventions

Aim 4: To analyze the effects of LIFT and REAP on pre- and post-liver transplant clinical outcomes.

BACKGROUND:

Frailty is defined as a biologic syndrome of decreased physiologic reserve and increased vulnerability to health stressors. The concept of frailty has recently emerged as a critical determinant in the field of cirrhosis and liver transplantation. Frailty impacts pre- and post-transplant clinical outcomes, including waitlist mortality, post-transplant mortality, frequency of hospitalizations and duration of hospital admissions. Although the impact of frailty in liver transplantation has been established in the literature, there is a lack of data supporting effective interventions to decrease frailty prior to liver transplantation. Moreover, the studies that have tested interventions to improve physical function have relied on frequent supervised physical therapy sessions and access to exercise equipment that it is not financially or logistically feasible for the majority of patients. Patient engagement in PT also remains a critical barrier to overcome to decrease frailty in preparation for liver transplantation. Developing a practical and effective intervention to consistently engage patients in physical activity and decrease frailty is essential to improving clinical outcomes in the pre- and post-liver transplant setting.

Our goal is to pilot test a novel PT intervention to decrease frailty in pre-transplant patients. We have designed a prototype “Liver FrailTy” intervention (LIFT) that includes: PT evaluation, an individualized home exercise prescription (HEP), daily text message reminders to exercise and weekly telephone check-ins with team members. We will also employ “Realistic Effort Action Planning” (REAP), a form of personality-informed motivational interviewing in a subset of patients to potentially enhance patient engagement and adherence to the home-exercise prescription.

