Our central hypothesis is that our LIFT (+/- REAP) intervention will 1) improve adherence to recommended levels of exercise in end-stage liver disease 2) reduce pre-transplant frailty and 3) will improve pre- and post-transplant clinical outcomes.

STUDY ENDPOINTS:

Primary endpoints:

- Frailty (measured by Liver frailty index [LFI])
- Clinical outcomes: placement on LT waitlist, waitlist-mortality, post-transplant mortality, post-transplant disposition (acute rehabilitation, subacute rehabilitation center, home, etc), number of hospitalizations, duration of hospitalizations, liver related complications (ascites, hepatic encephalopathy, variceal bleeding, hepatorenal syndrome, hepatopulmonary syndrome, infections).
- Feasibility (measured by 8-question emailed survey)

[figure not shown]
Secondary endpoints:

- Endurance (measured by the 4-meter walk test).
- Patient adherence to the home exercise prescription (measured by daily diary counts of adherence to prescribed exercises, tracked on the TrueCoach application)
- Degree of hepatic encephalopathy (measured by List Sort Working Memory [LSWM] test and the Flanker Inhibitory Control and Attention [FICA])
- Patient-reported quality of life (measured by various PROMIS questionnaires)
- Feasibility/acceptability (measured by a study-specific questionnaire evaluating the acceptability and feasibility as reported by patients, providers and support staff)

STUDY INTERVENTION(S) / INVESTIGATIONAL AGENT(S):

Home exercise prescription (HEP) detailed below in study design.

PROCEDURES INVOLVED:

Recruitment for Quality of Life Assessment Study:

- A Northwestern Medicine Enterprise Data Warehouse (NMEDW) search will be used to identify all patients who have been seen in Transplant Evaluation Clinic and are currently being considered for liver transplantation or are already on the waitlist or have received a transplant.
- Alternatively, a list of the patients described above will be obtained from the transplant coordinator.

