 - This is performed in all patients in clinic, regardless of whether they consent for this study specifically.
 - Time: 5 minutes
 - Appendix F
- Physical therapy introduction
 - Setting: in clinic or at bedside if inpatient.
 - Provide equipment (weights, therabands, dynamometer, Truecoach smart phone application if not installed over the phone after consent was received)

- Demonstrate initial home exercise prescription, which will include a set of exercises to be done at home on a daily basis (cardio exercises, resistance exercises). These recommended exercises will be within standard of care.
- Time: 10-15 minutes

LIFT subgroup:

Follow up:

- *Text reminders (every day):*
 - An automated system will be used to generate and send daily text messages reminding patients to follow their HEP. Texts will be standardized and not contain any PHI.
- *Exercise data collection (continuously):*
 - Data continuously collected via TrueCoach smart phone application to document adherence to exercise regimen. If patients are unable to appropriately track adherence on the smart phone application, this data will be collected at weekly videoconference/telephone check-ins detailed below.
- *LFI calculation at home (every 4 weeks)*
 - A dynamometer will be given to each patient at time of enrollment. A video will be uploaded on the TrueCoach application demonstrating how to perform grip strength testing.
 - Balance testing and chair stands will be tested at home.
 - A team member will walk patients through each test via a videoconference call.
- *Patient-reported quality of life assessment at home (every 4 weeks, surveys emailed - Patients will be called by a team member who will walk the patient through the survey and record data over the phone)*
 - Tools: PROMIS surveys: Physical function – Short form 8c, Cognitive Function
 - Data collected via REDcap
- *Personality assessment at home (every 4 weeks, survey emailed - Patients will be called by a team member who will walk the patient through the survey and record data over the phone)*
 - Tool: Modified Midlife Development Inventory (MIDI) Personality Scale
 - Data collected via REDcap
- *Videoconference/telephone check-in (every 1 week):*
 - Performed by a member of the research team.
 - If patients are unable to track adherence to exercise regimen via TrueCoach application, the team member will document daily physical activity on this call.

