 - If patients have questions regarding exercise regimen, they will be contacted by a physical therapist.
 - Progress reviewed and exercise regimen potentially adjusted by a physical therapist based on data collected and patient experience.
- *Clinical data collection via NEDW and review of EMR (every 4 weeks)*
 - Number of hospitalizations, intensive care unit admissions, duration of hospitalizations, development of decompensating events (ascites, hepatic

encephalopathy, variceal bleeding), transplant status, type of LT (living donor LT, simultaneous liver-kidney), duration of hospital admission for LT, duration of ICU admission for LT, duration of intubation post-LT, post-transplant discharge disposition, date of death, cause of death, post-transplant complications (rejection, infection, biliary complications).

- *Clinic visits (every 3 months, same tools as noted above)*
 - Patient-reported quality of life assessment
 - Hepatic encephalopathy assessment
 - Frailty assessment, 4-meter walk test (standard of care)
 - Physical therapy in person update (standard of care)
 - Data collection via NMEDW extraction and chart review: Number of hospitalizations, intensive care unit admissions, duration of hospitalizations, development of decompensating events (ascites, hepatic encephalopathy, variceal bleeding), transplant status, type of LT (living donor LT, simultaneous liver-kidney), duration of hospital admission for LT, duration of ICU admission for LT, duration of intubation post-LT, post-transplant discharge disposition, date of death, cause of death, post-transplant complications (rejection, infection, biliary complications).
- Feasibility assessment (for those who remain in the study for at least 1 month or until receiving a liver transplant; surveys emailed)
 - Tool: 8 -question survey emailed to eligible subjects as noted above.
 - Data collected via REDCap.
 - Time: < 3 minutes
 - Appendix G

All participants who enroll for the PT intervention will be randomized (1:1) into the LIFT subgroup or the LIFT + REAP subgroup at 2 weeks after enrollment/baseline session. The LIFT subgroup will continue to follow up as detailed above. The LIFT + REAP subgroup will undergo Realistic Effort Action Planning (REAP), which is described below:

LIFT + REAP subgroup:

Follow up:

- *REAP introduction (2 weeks after enrollment, via telephone/videoconference, time: 30 minutes)*
 - Performed by a member of the research team.

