- *Videoconference/telephone check-in (every 1 week)*
 - Performed by a member of the research team.
 - If patients are unable to track adherence to exercise regimen via TrueCoach application, the team member will document daily physical activity on this call.
 - If patients have questions regarding exercise regimen, they will be contacted by a physical therapist.
 - Progress reviewed and exercise regimen potentially adjusted by physical therapist based on data collected and patient experience.
 - REAP follow up (time: 5-15 minutes):
 - Reflect with patient on previous action plan and level of realistic sustained effort put forward in the past week.

- Encourage patient to adjust action plan according to perceived threshold of sustained effort.
- *Clinical data collection via NEDW and review of EMR (every 4 weeks)*
 - Number of hospitalizations, intensive care unit admissions, duration of hospitalizations, development of decompensating events (ascites, hepatic encephalopathy, variceal bleeding), transplant status, type of LT (living donor LT, simultaneous liver-kidney), duration of hospital admission for LT, duration of ICU admission for LT, duration of intubation post-LT, post-transplant discharge disposition, date of death, cause of death, post-transplant complications (rejection, infection, biliary complications).
- *Clinic visits (every 3 months, same tools as noted above)*
 - Patient-reported quality of life assessment
 - Hepatic encephalopathy assessment
 - Frailty assessment, 4-meter walk test
 - Physical therapy in person update
- Feasibility assessment (for those who remain in the study for atleast 1 month or until receiving a liver transplant; surveys emailed)
 - Tool: 8-question survey emailed to eligible subjects as noted above.
 - Data collected via REDCap.
 - Time: < 3 minutes
 - Appendix G

Audio/Video Recording:

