- Baseline clinical data will be collected at time of enrollment via the NMEDW and via chart review. Data will include: Age, gender, race, ethnicity, body mass index (BMI), employment status, education, marital status, etiology of liver disease, complications of liver disease (ascites, hepatic encephalopathy, presence of esophageal/gastric varices, history of variceal bleeding, hepatorenal syndrome, hepatopulmonary syndrome), liver frailty index scores, Karnofsky Performance Status Scores, MELD scores, medical history (coronary artery disease, chronic kidney disease, dialysis dependence, hypertension, hyperlipidemia), and baseline laboratory data (platelets, serum sodium, serum creatinine, PT/INR, total bilirubin, albumin, calculated MELD) (Appendix A, B)
- Personality assessment
 - o Setting: Surveys will be administered via Redcap. Survey links will be emailed to patients. Reminder emails will be sent if no response is received. Surveys may be completed over the telephone with a team member if no response is received to email, or if the patient requires assistance.
 - o Tool: Modified Midlife Development Inventory (MIDI) Personality Scale
 - o Time: 38 questions, 3-5 minutes
 - o Appendix C

- Patient-reported quality of life assessment
 - Setting: See setting of personality assessment above.
 - Tools: PROMIS surveys: Global 10, Physical Function, Cognitive Function, Fatigue, Pain, Dyspnea, Spiritual Health and Social Activities.
 - Time: ~34 questions, 10 minutes
 - Appendix D

Follow up:

- Personality assessment
 - Setting: Surveys will be administered via Redcap. Survey links will be emailed to patients. Reminder emails will be sent if no response is received. Surveys may be completed over the telephone with a team member if no response is received to email, or if the patient requires assistance.
 - Tool: Modified Midlife Development Inventory (MIDI) Personality Scale
 - Time: 38 questions, 3-5 minutes
 - Appendix C
- *Patient-reported quality of life assessment at home (every 4 weeks)*
 - Setting: See setting of personality assessment above.
 - Tools: PROMIS surveys: Global 10, Physical Function, Cognitive Function, Fatigue, Pain, Dyspnea, Spiritual Health and Social Activities.
 - Time: ~34 questions, 10 minutes
 - Appendix D
- *Data collection via NEDW and review of EMR (every 4 weeks)*

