 - Ability to provide consent will be assessed by the research team member introducing the research study and obtaining consent. Patients' capacity to consent will be assessed by asking the patients to clearly state the purpose of the study and what the study entails. They will be asked to outline the potential benefits and consequences of the study. They will be assessed on their understanding that the study is voluntary and their understanding that deciding not to participate will not impact their medical care negatively in any way.
 - If a participant is unable to provide consent, consent will be obtained from the participant's durable power of attorney for health care, court appointed guardian for health care decisions, spouse, and adult child, in this order.
 - If a patient is determined to not have capacity to provide consent, the research study will still be explained to the patient in a level suitable to their understanding.
- *Process to Document Consent in Writing*

PT Intervention participants

Please see Written Consent Form attached. This is the separate consent form for the LIFT+/- REAP study.

QOL Assessment participants

Please see the Verbal Consent form. This is the separate consent form for the QOL assessment study.

The researchers request a waiver of written consent for the QOL assessment study participants. The verbal consent form contains all elements of consent disclosure, and the QOL assessments are minimal risk. Interventions are limited to surveys and an EDW query of their medical records. These interventions would not require consent in a standard clinical context.

Moreover, the researchers have found that eConsent has not been practicable for the study population, which is generally elderly, chronically ill, and not technically savvy. As such, the researchers estimate that 30% of study candidates have been lost due to technical difficulties with the eConsent process.

PROTECTED HEALTH INFORMATION (PHI AND HIPAA)

- This study does involve the creation and use of PHI.
- HIPAA authorization will be obtained from all patients seen in Hepatology and Transplantation Evaluation Clinic, the setting in which participants are recruited.
- Specific PHI to be obtained from the EDW and chart review are outlined in Appendix A, B.
- QOL Assessment participants

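### The primary feasibility survey goes only to participants who stay at least 1 month or until transplant, and only by email, so the result is likely to be optimistic by an amount the documents cannot fix.

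*Combined protocol and SAP*

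**What the plan says.** The Objectives state "Aim 1: To evaluate the feasibility of the LIFT and REAP interventions in patients evaluated for liver transplantation". Study Endpoints lists, among the primary endpoints, "Feasibility (measured by 8-question emailed survey".

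Under Procedures Involved, the LIFT subgroup entry reads "Feasibility assessment (for those who remain in the study for at least 1 month or until receiving a liver transplant; surveys emailed", and the LIFT + REAP entry reads "Feasibility assessment (for those who remain in the study for atleast 1 month or until receiving a liver transplant; surveys emailed". The tool in both is an 8-question "survey emailed to eligible subjects as noted above". No reminder, telephone or in-clinic completion is stated for it.

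The PROMIS and MIDI home surveys in the same two arms are also emailed, but for those "Patients will be called by a team member who will walk the patient through the survey and record data over the phone". The separate Quality of Life study has a fallback too: "Surveys may be completed over the telephone with a team member if no response is received to email, or if the patient requires assistance".

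Randomisation to LIFT or LIFT + REAP takes place 2 weeks after the baseline session. The Statistical analysis paragraphs give no feasibility threshold, no treatment of missing surveys and no feasibility analysis.

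**The concern.** A feasibility result should describe the patients to whom the programme was offered. Here the rule for who is asked depends on staying, which is itself part of what feasibility means. According to Withdrawal of Participants, patients leave because they ask to, because stopping is judged best for their health and welfare, or, if cognitively impaired, because of undue distress. All of these reasons bear on feasibility, and also on the barriers that Aim 3 sets out to study.

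Email as the only mode adds a second, softer selection, because no other route is offered to a participant who does not respond. If both groups are less favourable than responders, the primary result is too high. A retention effect of REAP, which is intended to raise engagement, could then also hide or create a difference between arms.

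**Working it through.** **No figure to reproduce.** The protocol states no expected drop-out, response rate, scoring rule or target for feasibility. The check therefore sets the rules side by side and then shows a range under assumptions.

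**Who is asked**

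| Participant | Gets the feasibility survey? |
|---|---|
| Still in the study at 1 month | Yes, by email |
| Transplanted in week 1 | Yes, by email |
| Withdraws in week 3, no transplant | No |
| Eligible, does not answer the email | Sent, no stated follow-up |

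The second and third rows show that the rule is not simply one of minimum exposure.

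**Effect of omitting early leavers.** Let d be the share leaving in month 1 without transplant. Assume 85% of stayers and 40% of leavers are favourable. The plan reports 85%. The share among all enrolled is (1 − d) × 0.85 + d × 0.40.

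- d = 10%: 0.765 + 0.040 = 80.5%, overstated by 4.5 points
- d = 20%: 0.680 + 0.080 = 76.0%, overstated by 9.0 points
- d = 30%: 0.595 + 0.120 = 71.5%, overstated by 13.5 points

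If leavers were also 85% favourable, the overstatement would be 0 at every d.

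**Adding email non-response.** Let r be non-response among those eligible, and let pR, pN and pE be the favourable shares in responders, non-responders and early leavers. The all-enrolled share is (1 − d)[(1 − r)pR + r·pN] + d·pE, and the survey covers (1 − d)(1 − r) of those enrolled. A second set of assumed values takes pR = 80%.

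- d = 10%, r = 30%, pN = 60%, pE = 40%: 0.9 × (0.56 + 0.18) + 0.04 = 70.6%, overstated by 9.4 points, coverage 0.9 × 0.7 = 63%
- d = 30%, r = 30%, pN = 50%, pE = 0: 0.7 × (0.56 + 0.15) = 49.7%, overstated by 30.3 points, coverage 49%
- pN = pE = 80%: overstated by 0, whatever d and r

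At 63% coverage, with no assumption about the other 37%, the favourable share lies between 0.63 × 0.80 = 50.4% and 50.4% + 37% = 87.4%. The direction of bias is thus a judgement about who leaves, not a consequence of the rule alone.

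**Between arms.** The cut-off comes after randomisation. Apply the 85% and 40% values in both arms, and suppose 10% of those randomised are lost before 1 month in one arm and 30% in the other. Both arms would report 85%, while the all-randomised shares would be 80.5% and 71.5%. The survey would conceal a 9-point difference.

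**The case against.** Several stronger readings are tempting, and the documents do not support them.

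- **Less technical patients are excluded.** No rule does this. Every eligible participant is emailed, and entry to the PT study already requires a smart phone, tablet or computer with videoconferencing. The risk is non-response without a fallback.
- **The 30% loss measures email non-response.** It does not. The statement that "the researchers estimate that 30% of study candidates have been lost due to technical difficulties with the eConsent process" comes from the waiver request for the Quality of Life study and concerns consent. PT candidates lost at electronic consent never become participants. It shows that electronic steps are a known difficulty in this population, and no more.
- **Everyone who stops exercising is lost.** The criterion is remaining in the study. Non-adherence is not a listed withdrawal reason, so a participant who abandons the exercises without withdrawing should still be surveyed. Those lost are mainly formal early withdrawals and early deaths, and they may be few.
- **The arm comparison is biased.** The Statistical analysis section describes between-arm tests for clinical endpoints, and Study Endpoints lists feasibility separately from clinical outcomes. No feasibility test between arms is stated, so the harm arises only if one is made.

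It is also fair to say that a month in the study gives LIFT + REAP participants about two weeks of REAP to rate, and that the protocol has other evidence: a secondary feasibility/acceptability questionnaire with no stated stay restriction, and continuous adherence tracking with weekly calls as back-up.

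These arguments limit the size and certainty of the point. They do not repair the primary measure. Its own rule omits early withdrawals, no follow-up of non-responders is given for it, and the secondary questionnaire has no stated timing or mode.

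**Conclusion.** The point holds in a limited form. In both arms, participants who withdraw in month 1 without a transplant are never asked about feasibility, and those who do not answer the email have no stated telephone route. The primary feasibility result is likely to be optimistic, on the judgement that people who leave or do not reply are on average less favourable.

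A reader might infer that feasibility is certainly overstated, or by a known amount. The documents support neither. The 4.5 to 13.5 points rest on an assumed 10% to 30% early loss, assumed favourable shares of 40% and 85%, and an assumed yes/no scoring. The value is 0 if views are equal, and about 30 points in the most extreme scenario computed. Any feasibility comparison between arms would in addition depend on retention after randomisation.

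The change is worth making because it is cheap and concerns a primary endpoint.

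**What to change.** Change the feasibility entry in both follow-up lists so that every enrolled PT participant receives the 8-question survey at 1 month, at transplant or at withdrawal, whichever comes first. If there is no email response, offer completion by telephone at the weekly check-in or at the withdrawal contact.

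In the Statistical analysis section, state that:

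- overall feasibility is reported with all enrolled PT participants as denominator, since an all-randomised denominator would drop those who leave before week 2;
- any comparison between arms uses all randomised participants;
- response and retention are shown beside the result, with deaths and non-responders counted as separate categories;
- the mode of completion is recorded and reported.

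The cost is one changed sentence in each list, a short addition to the analysis section, and under 3 minutes per survey (the protocol's own estimate), largely on calls already planned. There are three small downsides. Some leavers will still not respond. Answers given by telephone to programme staff, on recorded calls, may be more favourable, which is why mode should be reported. Participants who leave before week 2 will have had no REAP to rate, so their answers inform overall feasibility only.

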 - Patients will be asked to reflect on their experience with the HEP.
 - Discussion of barriers to engaging in HEP and how to overcome them.
 - Reflection on past experiences with obstacles outside of exercise that required patients to exert a lot of effort and how they were able to accomplish it.
 - How can you apply these strategies to your exercise goals?
 - Introduce action plans.
 - Discussion of industriousness and how to apply learned industriousness to exercise-related goal achievement.
 - Discuss building increments to get to exercise goals.
 - Identify the threshold for sustained effort where patients can still reach their goal.

- Instruct patients to document level of effort for each day of exercise and refer to them as needed. Patients will document effort in TrueCoach application via comments section.
 - 1 = no exertion at all
 - 2 = very light
 - 3 = somewhat hard (but still feels OK to continue)
 - 4 = very hard (strenuous)
 - 5 = maximal exertion
- *Text reminders (every day):*
 - An automated system will be used to generate and send daily text messages reminding patients to follow their HEP. Texts will be standardized and not contain any PHI.
- *Exercise data collection (continuously)*
 - Data continuously collected via TrueCoach application to document adherence to exercise regimen. If patients are unable to appropriately track adherence on application, this data will be collected at weekly videoconference/telephone check-ins detailed below.
- *LFI calculation at home (every 4 weeks)*
 - A dynamometer will be given to each patient at time of enrollment. A video will be uploaded on the TrueCoach application demonstrating how to perform grip strength testing.
 - Balance testing and chair stands will be tested at home.
 - A team member will walk patients through each test via a videoconference call.
- *Patient-reported quality of life assessment at home (every 4 weeks, surveys emailed - Patients will be called by a team member who will walk the patient through the survey and record data over the phone)*
 - Tools: PROMIS surveys: Physical function – Short form 8c, Cognitive Function
 - Data collected via REDcap
- *Personality assessment at home (every 4 weeks, survey emailed - Patients will be called by a team member who will walk the patient through the survey and record data over the phone)*
 - Tool: Modified Midlife Development Inventory (MIDI) Personality Scale
 - Data collected via REDcap

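### Participants follow LIFT for two weeks before randomisation, but the arm comparisons have no stated time origin and the run-in adherence is not used

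*Combined protocol and SAP*

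**What the plan says.** The combined protocol and SAP describes the sequence under Procedures Involved. At the baseline session every PT intervention participant receives equipment, the TrueCoach application and a first home exercise prescription for daily use. Participants then "will be randomized (1:1) into the LIFT subgroup or the LIFT + REAP subgroup at 2 weeks after enrollment/baseline session".

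Two further statements imply that LIFT is already running by that point. After randomisation, "The LIFT subgroup will continue to follow up as detailed above". The REAP introduction, also set two weeks after enrolment, opens with an exercise review: "Patients will be asked to reflect on their experience with the HEP".

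Adherence is a secondary endpoint under Study Endpoints, "measured by daily diary counts of adherence to prescribed exercises, tracked on the TrueCoach application". The LIFT follow-up list adds: "Data continuously collected via TrueCoach smart phone application to document adherence to exercise regimen". Neither place gives a first day, a last day or a denominator.

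The Statistical analysis paragraph names chi-squared tests for categorical and t-tests for continuous clinical endpoints between the two subgroups. It does not name adherence and gives no other method for it. The multivariate analysis looks for factors associated with endpoints within each group, and the survival analysis adjusts for variables found significant in regression. No time origin is given for any of these analyses, and run-in adherence is not mentioned.

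**The concern.** REAP is meant to raise adherence to the exercise prescription, and LIFT against LIFT + REAP is the only randomised contrast in the study. REAP cannot affect days 1-14. With no time origin, an analyst may include those days in an adherence average, and may count hospitalisations or decompensations from a period when the patient had no arm.

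Two things are at stake. The first is dilution, which is strongest over short windows and in patients whose follow-up ends early through transplant, death or withdrawal. Because no window is fixed, the choice could also be made after the data are seen. The second is lost precision. Two weeks of each patient's own adherence under LIFT, recorded before assignment, is a natural baseline for this endpoint, and an unadjusted t-test ignores it.

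**Working it through.** **Inputs from the document.** Randomisation at 2 weeks; 1:1 allocation; adherence recorded daily; follow-up to 1 year after transplant, or up to 5 years if not listed (Study Timelines); sample size 500.

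**The plan's own figure.** The 500 cannot be reproduced: no alpha, power, effect size, SD or dropout is stated, nor how many of the 500 will be randomised.

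**Assumptions (none is in the document).** Two-sided alpha 0.05; 250 per arm; standardised difference d = 0.25; window lengths; run-in to post-randomisation correlation r; equal SDs for run-in and post-randomisation adherence.

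**Step 1: dilution of an average.** For a window of W weeks from enrolment, the run-in share is w = 2/W.
- A true difference in mean adherence, D, appears as (1 - w) x D.
- At a constant event rate, a rate ratio RR appears as w + (1 - w) x RR.

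The example takes 50% against 60% adherence after randomisation, 50% in both arms before it, and a true rate ratio of 0.80.

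| Window from enrolment | Run-in share | 10-point difference appears as | RR 0.80 appears as |
|---|---|---|---|
| 4 weeks | 2/4 = 50% | 5.0 | 0.900 |
| 12 weeks | 2/12 = 16.7% | 8.3 | 0.833 |
| 26 weeks | 2/26 = 7.7% | 9.2 | 0.815 |
| 52 weeks | 2/52 = 3.8% | 9.6 | 0.808 |

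At 5 years (260 weeks) the share is 2/260 = 0.8%.

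**Step 2: total counts.** Over 84 days from enrolment, expected exercise days are 14 x 0.5 + 70 x 0.5 = 42 on LIFT and 14 x 0.5 + 70 x 0.6 = 49 on LIFT + REAP, a difference of 7. Over the 70 days from randomisation they are 35 and 42, again a difference of 7. The run-in adds variance to a difference in totals but does not shrink it.

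**Step 3: power for an average.** The standardised effect is multiplied by (1 - w) / sqrt(w^2 + (1 - w)^2 + 2w(1 - w)r). Counted from randomisation, power is 79.8%. Counted from enrolment, with r from 1.0 down to 0.3:
- 4 weeks: 29% to 41%
- 12 weeks: 64% to 74%
- 26 weeks: 73% to 78%
- 52 weeks: 77% to 79%
- 5 years: about 79%

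**Step 4: using the run-in as a covariate.** ANCOVA multiplies the residual variance by 1 - r^2. Unadjusted, n per arm for 80% power is 2 x (1.960 + 0.842)^2 / 0.25^2 = 251.2, so 252.

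| Assumed r | Variance removed (r^2) | Power at 250 per arm | n per arm for 80% power |
|---|---|---|---|
| 0.3 | 9% | 83.4% | 229 |
| 0.5 | 25% | 89.8% | 189 |
| 0.7 | 49% | 97.5% | 129 |

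This gain is measured against an unadjusted comparison already counted from randomisation, so it does not depend on any dilution having occurred.

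**The case against.** A reader might infer that the endpoints run from enrolment and that run-in days and events are counted in the arms. The document does not say so. The endpoint list and the Statistical analysis paragraph are silent on time origin. Continuous capture describes data collection, not an analysis window. The LIFT + REAP follow-up list opens with the week-2 session, so counting from randomisation fits the text equally well. This objection stands: the documented gap is the missing origin, not a wrong one.

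Further limits also stand.
- The endpoint is worded as counts, and a difference in total counts is not diluted.
- Follow-up can be long, and dilution is about 4% at 52 weeks and under 1% at 5 years.
- The run-in is common to both arms, so the effect is attenuation towards zero whichever arm is ahead, not bias towards one arm.
- Nobody randomised can have died before week 2, so those deaths cannot fall in an arm. A survival clock started at enrolment would add two event-free weeks to both arms.
- The enrolment liver frailty index (LFI) is a valid pre-randomisation baseline. The new baseline exists for adherence only, because no week-2 frailty, quality-of-life or cognitive measurement is listed.
- Post-transplant endpoints naturally start at transplant.
- Randomising after two weeks has a purpose, since REAP draws on the patient's exercise experience. Nothing here argues against it.

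The covariate could be called an efficiency preference resting on assumed correlations. That is fair as to the size of the gain. But the data are already collected, and the plan proposes nothing better than an unadjusted test.

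**Conclusion.** The point holds in limited form. A two-week common LIFT period before randomisation is clearly implied, no time origin is given for the arm comparisons, and run-in adherence has no planned use. Whether dilution occurs depends on a choice the plan leaves open. If adherence is averaged from enrolment, dilution is serious at 4 weeks (half the difference), moderate at 12 weeks (a sixth) and small from 26 weeks on. The firmer gain is in precision: 9% to 49% of residual variance for r between 0.3 and 0.7. The run-in shares follow from the stated two weeks once a window is chosen. The windows, effect sizes, arm size and correlations are assumptions. The point concerns the adherence comparison and the non-fatal event counts, and does not call the primary frailty comparison into question.

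**What to change.** In the Statistical analysis paragraph:

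1. Start the LIFT against LIFT + REAP comparisons of adherence, hospitalisations, decompensations and survival at the date of randomisation. Keep transplant as the origin for post-transplant endpoints.
2. Report days 1-14 separately as the run-in, including how many patients leave before randomisation.
3. Replace the unadjusted t-test for adherence with a linear model (ANCOVA) of post-randomisation adherence, with arm as the factor and the patient's run-in adherence as covariate. State the window and denominator for both.

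The cost is wording. Adherence is already recorded daily, so no new collection is needed. Fourteen days per patient leave the outcome, but REAP cannot affect those days, and for adherence they return as the covariate.
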